Fifty adverse events (AEs) were reported until the end of the 3-month follow-up. Two SADEs were reported in two patients with risk of erosion and subsequent explantation of the BioMonitor 2. The SADE-free rate was statistically significant higher than 90%. The primary endpoint was met.

The mean R-wave amplitude at the 1-week follow-up visit was 0.75 mV and demonstrated significant superiority to the R-wave amplitude of the predecessor BioMonitor (0.3 mV). Thus, the secondary endpoint was met. Moreover, the BioMonitor 2 showed a low and stable noise burden, which had a mean value of 3.0% and 3.4% at the 1-week and 3-month follow-up, respectively.

All endpoints were met. The study results confirm the safety and efficacy of the BioMonitor 2 system and show that the insertion procedure performance was overall rated between 'good' and 'acceptable' by the investigators^{22,23}. A publication has been accepted⁶⁴.

⁵ Clinical Investigation Report of the BIO|Master.BioMonitor 2 Study of the Implantable Cardiac Monitor BioMonitor, Version 1.0. 2017

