Secondary endpoint 1 and 2 for the BIOMONITOR III evaluate the efficacy of the ICM's appropriate sensing. Compared to predecessor devices, the changes in size and tip might change the characteristics of the electrical contact of and the electrical potential between the poles. It is expected that the R-wave amplitude will be slightly reduced because of a shorter distance between the sensing electrodes. Therefore the R-wave amplitude and noise burden will be assessed.

Secondary endpoint 3 evaluates the P-wave visibility as assessed by the investigator. P-wave detection helps to support the identification of correctly detected and classified episodes. For physicians, the presence or absence of the P-wave and its distance from the R-wave on an ECG is very important information for the interpretation of an ECG. The assessment is based on the evaluation of the ability of a physician to recognize P-waves in the stored sECGs of the BIOMONITOR III as a diagnostic criterion.

Secondary endpoint 4 evaluates the SADE-free rate related to the BIOMONITOR III 12 months after insertion to confirm the safety of the BIOMONITOR III system from insertion until

the 12-month follow-up. Due to suggestions of the notified body to cover a large proportion of the life-time of the devices, the follow-up duration for the study was extended to 12 months as compared to 3 months. However, the study duration does not cover the entire life-time of the devices and therefore, additional measures will be taken to comply with the active PMCF requirements for e.g. Post-Market Surveillance activities.

Further data of interest are collected to assess arrhythmia detection and the insertion procedure of the BIOMONITOR III (see section 7.5).

Data from insertions and follow-ups are recorded in eCRFs, supplemented by clinical and device data collected through Home Monitoring. Home Monitoring allows for the reliable and continuous collection of many parameters directly as source data. By combining the Home Monitoring data with the clinical data from eCRFs, comprehensive information on BIOMONITOR III is available for analysis.

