7.1.2 Secondary objectives

Secondary objectives are to verify the sensing performance of the device by evaluating the R-wave sensing amplitude, noise burden and P-wave visibility. Another secondary objective is long-term safety over 12 months.

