8.1.3 Selection of measurements for endpoints

For the primary endpoint, the SADE-free rate will be assessed by collecting and evaluating adverse events until the 3-month follow-up (see section 7.2.1).

For **secondary endpoint 1**, the R-wave is measured via the programmer. Due to its automatic measurement, this figure unambiguously indicates the device's ability to detect the patient's heart beats. The noise burden for **secondary endpoint 2** is continuously recorded by the device. The value retrieved from the device with the help of the programmer clearly measures the time during which the device is unable to detect the patient's heartbeats.

P-waves are not detected by the device; therefore, the investigators decide whether P-waves are visible in a test ECG. A periodic sECG was chosen as the sample ECG because during arrhythmia, P-waves are often not present. The P-wave visibility (**secondary endpoint 3**) is determined by counting P-waves and QRS-complexes.

For the **secondary endpoint 4** the long-term safety of the BIOMONITOR III system, all SADEs related to the BIOMONITOR III system are collected by the investigators and evaluated by an internal adjudication board as described above. An observation period of 12 months was chosen to significantly extent the monitoring period for safety events beyond the 3 months which are defined for the primary endpoint.

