9 STUDY PROCEDURES

9.1 Overview

The following study related procedures (Table 3) apply and have to be documented in the respective electronic case report form (eCRF) for each patient enrolled. Subsequent to the enrollment and the insertion of the investigational device, three follow-up visits are scheduled - 1st follow-up after 10 days to 4 weeks after insertion, after 3 months and 12 months after insertion (\pm 14 days). A 48-hour Holter ECG is applied during the 1st follow-up procedure (10 days to 4 weeks after insertion at the latest).

The visits need to take place within a certain time frame as listed in Table 3. However, if circumstances prevent a protocol conform timing of the follow-up, the follow-up shall be performed anyhow and the reason for the protocol violation has to be indicated on a CIP deviation form. If circumstances prevent the presence of the patient at the follow-up visit, the reason for the missed follow-up has to be indicated on the eCRF.

Table 3: Overview of study procedures.

Investigations	Enrollment/Baseline	Insertion	1 st follow-up (10 days to 4 weeks after insertion)	48-hour Holter- ECG	Month 3 (\pm 14 days)	Month 12 (\pm 14 days)
Patient informed consent	x					
Verification of in- and exclusion criteria	x					
Demographics and medical history	x					
Indication for ICM	x					
Medication log	x	x ¹	x ¹		x ¹	x ¹
Insertion of BIOMONITOR III: Information on procedure and assessment of insertion procedure and tool handling		x				
Check of insertion location (wound check)			x		x	
Rating of wearing comfort (after wound healing)			x		x	
Migration of BIOMONITOR III			(x)		(x)	(x)
Explantation of BIOMONITOR III			(x)		(x)	(x)
R-wave measurements (highest and lowest value amplitude)	x	x			x	x
P-wave visibility assessment			x		x	x
Noise burden (%)			x		x	x
Program settings (ProgramConsult and SensingConsult)			x		x	x
Usage of indication-based program sets	x	x			x	x
Program periodic subcutaneous ECG (cycle duration 1 day 'daily')	x					
Program periodic subcutaneous ECG (cycle duration 30 days 'periodic')			x			
Changes in device programming			(x)		(x)	(x)
Device interrogation and electronic data file up-load via ReportShare	x	x			x	x
Apply Holter ECG and read out Holter ECG recordings after 48 hours				x		

Provide CardioMessenger (mandatory) and Remote Assistant III (optional, incl. test of Remote Assistant III)	x				
Activation of Mome Monitoring and registration at the Monitoring Service Center	x				

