- Inspect the trend values for the R-wave amplitude (see section 9.5.1) and noise burden (see section 9.5.2) at each regular follow-up visit.
- Adjust patient specific program parameters, if applicable. Use the indication specific program settings (Go to 'Parameters' - 'Program sets' - 'ProgramConsult') if possible.
- **1st follow-up:** Program the periodic subcutaneous ECG recording in the 'Patient profile' tab of the HMSC and change cycle duration to 30 days.
- Store the electronic procedure data (including final device settings, measurements) of the BIOTRONIK programmer. Provide the programmer data by uploading the PDF-File via the ReportShare-function (see 4.7.1.11 and 9.5.4).
- P-wave measurements within the HMSC as described in section 9.5.3.
- **1st and 3-month follow-up:** ask the patient to answer the questions regarding the wearing comfort of the BIOMONITOR III
- **1st and 3-month follow-up:** check of insertion location and device migration (if applicable).

¹⁰ Problem means any deficiency of the programmer or software or any adverse events related to the use of the programmer.

- Ask the patient to answer the questions regarding the usability of the Patient App, if applicable.
- Provide further details in case the patient was diagnosed (concerning the medical indication for the BIOMONITOR III).
- Answer questions regarding programmer and programmer software handling and document possible problems¹¹ regarding device programming.
- Answer questions regarding possible examinations by imaging techniques (MRI, mammography).
- Ensure that all source data from the 1st, 3-month and 12-month follow-up are documented, e.g. using a source data sheet which is recommended, and enter data in the respective eCRFs in the iMedNet EDC database.
- Document any adverse event or device deficiency observed during the follow-up by using the respective eCRF. Please adhere to the reporting timelines listed in section 18.

9.5 Description of measurements and other procedures performed at insertion and follow-up visits

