### 15.2.4 Data of interests derived from the FU-CRFs and the CRF "Deactivation/Explantation" and FU

This includes the following data of interest:

- Assessment of BIOMONITOR III migration (if applicable)

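### Section 9.4 and Table 3 disagree on a month-12 migration check, and neither schedules an insertion-site check at that long-term safety visit

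*Protocol*

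**What the plan says.** **Purpose of the 12-month visit.** Protocol section 7.1.2 states: "Another secondary objective is long-term safety over 12 months". Section 5.3 explains that "the follow-up duration for the study was extended to 12 months as compared to 3 months", following suggestions from the notified body. Section 8.1.3 gives the same reason for secondary endpoint 4: "An observation period of 12 months was chosen to significantly extent the monitoring period for safety events beyond the 3 months". Under sections 9.4 and 9.9 the visit takes place in the office and ends regular participation.

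**What is examined.** Section 9.4 has one bullet, headed for the 1st and 3-month follow-ups, that reads "check of insertion location and device migration (if applicable". In Table 3 (section 9.1) the row "Check of insertion location (wound check" is marked at the 1st and 3-month follow-ups and is blank at month 12. The row "Migration of BIOMONITOR III" carries an if-applicable mark at the 1st, 3-month and 12-month follow-ups.

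**What the SAP uses.** Section 15.2.4 lists "Assessment of BIOMONITOR III migration (if applicable" among the items taken from the follow-up forms and the deactivation/explantation form, without naming visits.

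**The concern.** There are two faults. First, section 9.4 and Table 3 give sites different instructions on migration at month 12. A site that works from the text and a site that works from the table would return different data, and a blank could mean no migration or not assessed.

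Second, the visit added to observe safety for longer omits the site check made at the two earlier visits. Several of the anticipated complications in sections 6.2.1 and 18.7 are local: erosion, dehiscence or protrusion, infection and migration. In the predecessor's master study (section 5.2.4), "Two SADEs were reported in two patients with risk of erosion and subsequent explantation of the BioMonitor 2". A threatened erosion that the patient has not noticed could pass unrecorded at the last visit, with no later scheduled visit to find it. Under-recording of this kind can only make the 12-month result look better.

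**Working it through.** **1. The plan's own figure.** The sample size in section 11.2 reproduces. The normal approximation gives 132.8, so 133, and 133/0.9 = 147.8, so 148. By the exact binomial test, n = 141 allows at most 7 patients with an event, with one-sided alpha 0.0242 and power 0.937. Then 141/0.9 = 156.7, so 157. These figures concern the 3-month endpoint, and nothing below changes them.

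**2. The sources side by side.**

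| Item | Section 9.4 | Table 3 | SAP 15.2.4 |
|---|---|---|---|
| Insertion-site check | 1st, month 3 | 1st, month 3 | not covered |
| Migration, if applicable | 1st, month 3 | 1st, month 3, month 12 | follow-up forms, visits not named |

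The site-check row is consistent, and month 12 is missing from it. The migration row is contradictory, and the SAP does not resolve it.

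**3. What else would pick up a late site problem.**
- Section 5.3: adverse events and device deficiencies are asked about at every follow-up. Section 9.4 has them documented, with no restriction by visit.
- Section 18.9: serious events are reportable within 24 hours of detection, outside scheduled visits too, including those learned of from other departments and facilities.
- Table 3 and section 9.7: explantation is recorded at month 12 where applicable and has its own form.

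These routes should capture anything symptomatic, treated or explanted. What remains is change that nobody has noticed and, if section 9.4 governs, migration.

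**4. Can the size be derived?** Three figures are available, and none of them gives it.
- Predecessor: 2 of 90 inserted patients, 2/90 = 2.2%. Both events were reported within 3 months, so they say nothing about later ones.
- Table 4: erosion and dehiscence at 1 to 10 per 100. Applied to 157 patients this is 1.6 to 15.7, but it counts adverse events of any seriousness, with no split before and after month 3.
- One missed patient: 1/141 = 0.7 percentage points. But 141 is the evaluable number for the 3-month test. SAP sections 14.1 and 14.5 use a Kaplan-Meier estimate at 365 days on all patients, where the step depends on the number still at risk, which is not known in advance.

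**5. Illustration with assumed values.** If a share r of 141 patients had a late site change and a share s of these were recorded, the chance of recording none is (1 − r·s)^141. For r = 1% this is 24% at s = 1 and 49% at s = 0.5. For r = 2% it is 6% and 24%. The documents give neither r nor s. The lower value of s is meant for silent site changes, not for SADEs, which have the other routes in step 3.

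**The case against.** The strongest reply is that ascertainment is already adequate. A SADE must meet a seriousness criterion (sections 18.4 and 18.5), and late erosion that led to hospitalisation or explantation would normally be known through the routes in step 3. Migration by itself is a data-of-interest item. Section 5.3 argues that most complications come early, and the table labels the site item as a wound check, so stopping it at 3 months has a rationale. The first-generation master study, with one year of observation in 152 patients, reported no device-related and four procedure-related SADEs (section 5.2.1). Secondary endpoint 4 carries no hypothesis, and success of the study rests on the primary endpoint alone.

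Most of this stands, and it rules out several stronger readings that a reader might infer:
- That nothing is assessed after month 3, or that patients leave unexamined. The documents show an in-office visit with device interrogation and adverse-event enquiry.
- That erosion is the main SADE to expect after month 3. Two early events with a different device do not show this.
- That the 12-month rate is inflated by a stated number of points. Step 4 shows that no such figure follows.

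There is also a separate defect. SAP section 14.2 uses the primary-endpoint flag for the 12-month analysis, and under SAP section 10.1 that flag requires all conditions of protocol section 7.2.1, which exclude SADEs after the 3-month follow-up. Read literally, a late SADE would not count even if it were found. That needs its own correction and does not enlarge this point.

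The reply does not remove the contradiction on migration. Nor does it explain why general enquiry suffices at month 12 when the plan added a specific site check to it at the two earlier visits. The early-complication argument supports a 3-month primary endpoint. It does not support leaving the site check out of a visit whose stated safety purpose is later events.

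**Conclusion.** The point holds as a modest, inexpensive improvement. Section 9.4 and Table 3 conflict on migration at month 12. Neither schedules an insertion-site check at the only scheduled visit after month 3. The exposure is confined to silent or mild late site changes, including threatened erosion not noticed by the patient, and to migration if section 9.4 governs. Any effect on the 12-month SADE-free rate would be in the favourable direction, but its size cannot be derived from the documents. The 3-month primary endpoint, its test and the sample size of 157 are unaffected.

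This rests on reading Table 3 as two marks for the site check and three for migration. The case report forms are not among the documents, so the 12-month form may already hold one or both items. If it does, the protocol text still has to be brought into line.

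**What to change.** 1. Reconcile section 9.4 and Table 3 on migration at month 12, and have SAP section 15.2.4 name the visits that supply the data.
2. Extend the existing insertion-site check to the 12-month visit in section 9.4, in Table 3 and on the 12-month form, so that ascertainment for secondary endpoint 4 matches the earlier visits. If the sponsor prefers not to, the protocol should state how the site is ascertained after month 3.

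The cost is a brief inspection at a visit already held in the office and one form item, presumably one already in use at the earlier visits. The 12-month result may become slightly less favourable.

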9.5.1 R-wave measurement

The R-wave amplitude shall be measured after insertion and during all follow-up visits (see section 9.3.1 and 9.4). The following steps need to be performed:

- Freeze, store and print the sECG window. In case of varying amplitude labeling, document both, the lowest and the highest amplitude value in the eCRF (Figure 11 and Figure 12).

[figure not shown]

Figure 11: Freeze screen during interrogation.

[figure not shown]

Figure 12: Document R-wave amplitude based on programmer screen or printout.

¹¹ Problem means any deficiency of the programmer or software or any adverse events related to the use of the programmer.

Note: It is possible that sensing is compromised by noise/artefacts immediately after the insertion procedure due to electrolytic properties of the anesthetics. In such a case it is advised to wait until the anesthetics have dissolved (~1-2 hours).

9.5.2 Measurement of noise percentage

The noise percentage shall be determined during all follow-up visits (see section 9.4). The following steps have to be performed:

- Go to 'Diagnostics' → 'Sensing' → 'Noise duration trend'. Put the caliper on the date of follow-up visit. Print. Document the noise percentage of the day of the follow-up visit.
- Freeze, store and print the sECG window as described in 9.5.1.

9.5.3 Assessment of P-wave visibility

The P-wave visibility shall be measured during all follow-up visits (see section 9.4). Assessment of P-wave visibility within the HMSC need to be performed as follows:

1st follow-up

At the day of 1st follow-up, check the first periodic sECG episode that was successfully transmitted to the HMSC. In patients with sinus rhythm, evaluate the number of expected P-waves (i.e. number of complete heart cycles) and P-waves that can undoubtedly be identified.

Check also the latest periodic sECG episode which was successfully transmitted to the HMSC.

In patients with sinus rhythm, evaluate the number of expected P-waves (i.e. number of complete heart cycles) and P-waves that can undoubtedly be identified.

3-month and 12-month follow-up

Check the periodic sECG episode which was successfully transmitted to the HMSC and, which is closest to the 3-month and 12-month follow-up date.

In patients with sinus rhythm, evaluate the number of expected P-waves (i.e. number of complete heart cycles) and P-waves that can undoubtedly be identified.

Enter the dates and values in the follow up SDS. Provide a PDF file export (StatusReport) from the HMSC with the respective episodes and upload the PDF-Files via ReportShare. Alternatively, the PDF files can be sent to the study e-mail address [REDACTED]

In addition an independent core laboratory will compare the P-wave visibility between the 48-hour Holter-ECG device and the sECG from the BIOMONITOR III. For this, the investigational site needs to conduct a 48-hour Holter-ECG and BIOMONOITOR III read out according to section 9.6.

9.5.4 Data Transfer via Report Share

During the study, programmer data containing all measurements have to be provided to the sponsor for insertion and each follow-up. Furthermore programmer data should be provided also for interim visits of the patient at the study site.

Note: We strongly recommend using Report Share function to facilitate the data transfer to BIOTRONIK.

Automatic export

Pre-setting of Renamic Programmer: open the 'Options' dialog in the Data Manager.

Activate the automatic upload by enabling the 'Automatic export' (3) checkbox (see Figure 13).

After implantation or FU was performed: click 'end' to close the application.

The upload will start automatically.

Or Manual export

Pre-setting of Renamic Programmer: open the 'Options' dialog in the Data Manager.

Activate the manual upload by enabling the 'HMSC export' (2) checkbox (see Figure 13).

Select one follow-up from Data Manager.

Click on 'Preview' and select all checkboxes.

Click on 'Export'.

[figure not shown]

Figure 13: Interface for the export of programmer data to HMSC via ReportShare.

In case that ReportShare is not available, e.g. for organizational or technical reasons, the following alternatives may be used for delivery of programmer data:

- Delivery via email to [REDACTED]
- Delivery via USB flash drive

For every export it has to be ensured that data are pseudonymized.

9.6 48-hour Holter ECG recording

48-hour Holter ECGs are to be recorded from all patients. It is recommended to start recording immediately after the completion of the 1st follow-up.

9.6.1 Initiation (start day)

1. Preparing the BIOMONITOR III

- Set the clock on the programmer device to the precise local time.
- Delete statistics and episodes ('Recordings' → 'Restart'). This sets the clock of the BIOMONITOR III.

2. Preparing the Holter ECG

- Label flash card with patient ID and date.
- Insert batteries (take a new one for every patient!).
- Insert Flash card.

- Set the clock of the Holter ECG device to the precise local time (via 'Set up' → Time; navigate with yellow button and enter with green button).
- Select 'Start Week' via menu.
- Speech recording (in menu select 'record' and enter with green button).

3. Applying the Holter ECG device

- Attach three ECG electrodes according to Figure 14.

[figure not shown]

Figure 14: Electrode position for Holter ECG.

- Ensure ECG does not alter with change in position/posture.
- Reposition electrodes in case of ECG instability/poor quality.
- Start recording (with green button).
- ECG signal can be displayed by simultaneous pressing of the green and yellow button.
- Use neck lanyard, shoulder pouch or belt clip to attach recorder.

9.6.2 Completion (after 48-hours, end day)

1. Removing the ECG-device

- Stop recording by pressing the green button.
- Detach electrodes and remove ECG recorder.
- Remove battery and CF card.

2. Interrogate BIOMONITOR III

3. Providing data to the sponsor

- Download programmer data on USB stick (xml und pdf) and upload the PDF-Files via ReportShare. Alternatively, the PDF files can be sent to the study e-mail address [REDACTED]. Make sure the PDF file contains the "episode list".
- Send CF Card to:
[REDACTED]

BIOTRONIK SE & Co. KG
Center for Clinical Research
[name]
[name], Germany

